2.4 ANALYSIS TIMING

The efficacy and safety data will be reported at the end of the study, following database lock. Database lock will occur once the final SAP has been approved

and the database is clean. The analysis population datasets will then be created and reviewed prior to release of Treatment Allocation Information (TAI).

3. STUDY CONDUCT

3.1 RANDOMIZATION

Patients will be randomized 1:1 to conventional oseltamivir or double dose oseltamivir, stratified according to 4 binary stratification factors. Patients randomized under Protocol versions A and B will be stratified according to transplant (SOT vs. HSCT); time between onset of influenza symptoms and treatment start (≤ 24 hours vs. > 24 hours); influenza vaccination status for current influenza season (yes vs. no), and age (≤ 12 years vs. > 12 years).

Patients randomized under Protocol C onwards will be stratified according to transplant (yes vs. no), time between onset of influenza symptoms and treatment start (up to 96 hours, ≤ 48 hours, > 48 hours), influenza vaccination status for current influenza season (yes vs. no) and by age (≤ 12 years vs. > 12 years). As only transplant patients were enrolled during Protocol A and B, at this time, the randomization was not stratified by transplant status.

The master randomization list is an un-stratified randomization list implemented in the Interactive Voice/Web Recognition System (IxRS) using a dynamic block allocation algorithm to centrally assign patients to the correct strata.

Following the release of TAI, the treatment assignments from the IxRS listing will be checked against the master randomization list to ensure the correct treatments have been assigned. Furthermore, the date and time of randomization will be checked against the date and time of first dose to ensure patients were randomized prior to receiving treatment. Any errors noted will be listed as protocol deviations in the clinical study report (CSR).

Any patients who were assigned to the incorrect strata level at randomization will have the strata information corrected for reporting purposes but the original randomization will remain unaltered.

3.2 INDEPENDENT REVIEW FACILITY

Not applicable.

3.3 DATA MONITORING

Blinded reviews of the data will be performed on an ongoing basis by the study scientist.

4. STATISTICAL METHODS

All analyses, summaries and listings will be performed using SAS[®] software (version 9.2 or higher) in a UNIX environment. The data will be listed in the CSR.

All endpoints previously defined will be listed and summarized using appropriate descriptive statistics.

4.1 ANALYSIS POPULATIONS

The main analysis populations are defined below.

4.1.1 Intent To Treat (ITT) Population

All patients randomized will be included in the ITT population. Patients will be summarized under the treatment to which they were randomized. This population may be used to summarize efficacy endpoints for the purpose of sensitivity analyses. This population will generate the most conservative effect estimates because there may be allocation errors, non-infected patients and/or non-adherence to treatment.

4.1.2 Intent To Treat infected (ITT_i) Population

All patients randomized and with central laboratory confirmation of influenza infection, excluding patients infected with oseltamivir-resistant influenza at baseline, will be included in the ITT_i population.

4.1.3 Modified Intent To Treat infected (mITT_i) Population

All patients randomized to a particular treatment, regardless of whether they received that treatment or not, and received at least one dose of study drug and with central laboratory confirmation of influenza infection, excluding patients infected with oseltamivir-resistant influenza at baseline, will be included in the mITT_i population. This population will also be used to summarize all efficacy and resistance endpoints because it will render least biased effect estimates. This population was not defined in the protocol.

The definition of oseltamivir-resistant influenza at baseline is defined in Section 2.2.6. Decisions on patient exclusion from the ITT, ITT_i and mITT_i population sets will be made by the statistician and study scientist after database closure. Excluded patients will be documented along with the reason for exclusion.

4.1.4 Pharmacokinetic-Evaluable Patient Population

The Pharmacokinetic Evaluable Patient (PKEP) population comprises all patients in the ITT population have at least one post-dose drug concentration measurement at a scheduled visit time point. Patients may be excluded from the PKEP population if they significantly violate the inclusion or exclusion criteria, deviate significantly from the protocol, or have unavailable or incomplete data that may influence the PK analysis.

Decisions on patient exclusion from the PKEP will be made prior to database closure by the clinical pharmacologist based on information supplied by the Data acquisition specialist (whether patients in the ITT population have at least one post-dose drug concentration measurement at a scheduled visit time point). No

PK data will be shared with the team as this would unblind the study. Excluded patients will be documented along with the reason for exclusion.

4.1.5 Safety Population

The safety analysis population will include all patients who receive at least one dose of study drug and have had a safety assessment performed post randomization. All safety variables will be summarized and presented in tables based on this safety population. Any patients who receive a dose that differs from the dose to which they were randomized will be reported under their actual treatment.

4.1.6 Protocol Deviations

Major protocol deviations will be listed in the CSR. Major protocol deviations will include those captured during the study conduct (██████ file), as well as any additional deviations found as a result of programmatic checks of the following criteria:

- Patients who received their first study drug dose more than 96 hours from onset of symptoms.
- Patients with randomization errors – randomized and not dosed, dosed prior to randomization.
- Use of antiviral treatment for influenza in the 2 weeks prior to randomization and during the 10 day treatment phase of the study.
- Less than 16 of the 20 planned doses (80%) of study drug.

Sensitivity analyses may be carried out excluding any major protocol deviations.

4.2 ANALYSIS OF STUDY CONDUCT

The following tables will be summarized by treatment group according to current sponsor data standards.

- Summary of treatment.
- Summary of disposition of patients in the Safety, ITT, ITTi, mITTi and PKEP populations.
- Summary of patients excluded and reasons for exclusions from each of the analysis populations (Safety, ITT, PKEP, ITTi, mITTi).
- Summary of withdrawals, including the reason for withdrawal (Safety, ITT, ITTi, mITTi).
- Summary of concomitant medications split by: immunosuppressive treatment; treatment for influenza-like symptoms; treatment for AEs; other treatments.

Protocol deviations, as reported directly by sites or captured through programmatic checks of the database of deviations that occur during study

conduct, will be listed and summarized by randomized treatment accordingly, as per Section 4.1.6.

4.3 ANALYSIS OF TREATMENT GROUP COMPARABILITY

Baseline patient characteristics will be summarized by treatment group. The main population for these baseline summaries will be the mITTi. However, summaries based on the Safety, ITT and ITTi populations will also be included in the CSR.

All baseline patient characteristics data will be listed. To assess comparability, descriptive statistics will be presented by treatment group as follows:

- Demography including age, gender, race and ethnicity.
- Immunodeficiency conditions at baseline.
- Transplant history.
- Historical CD4 count.
- Influenza vaccination status.
- Previous or current diseases at baseline (Medical History).
- Previous treatments, split by immunosuppressive treatment, treatment for influenza-like symptoms, and others.
- Influenza infection status: Flu Type (A or B) and Flu A subtype (H1N1, H3N2) (mITTi only).

No statistical comparisons will be made, as no formal hypothesis is being tested.

4.4 EFFICACY ANALYSIS

All efficacy endpoints are considered secondary or exploratory. As no formal efficacy hypothesis is being tested, treatment differences presented in any efficacy analyses will be reported with associated confidence intervals (CIs) only. Efficacy endpoints will be summarized by age group. All summaries and analyses are described below and listed in [Appendix 5](#). All efficacy analyses will be based on the mITTi and ITTi populations. ITT will be presented for the main efficacy TTR summary tables (all symptoms and temperature only) to investigate the effect of treatment in a “real world” scenario, i.e. unknown infection status and/or adherence. N.B. Regulatory bodies have asked for these outputs in pivotal studies.

All efficacy summaries and analyses will be carried out separately for adults (patients ≥ 18 years) and paediatrics (patients <13 years old). Adolescent data (patients aged between ≥ 13 and <18 years old) will be listed as appropriate.

As the symptom data are recorded on patient diaries, data errors cannot be queried. Obvious data errors, i.e. temperature 100°C , will be excluded and documented. For duplicated data, the worst evaluation will be used to obtain conservative estimates.

The endpoints as described in the protocol have been expanded to give sufficient information of the derivations required, e.g. *symptom scores* was the endpoint defined in the protocol but *Time To Resolution of symptom scores* is how it is described in the SAP.

4.4.1 Primary Efficacy Endpoint

Not applicable.

4.4.2 Secondary Efficacy Endpoints

4.4.2.1 Time to Event Endpoints

Time to event endpoints include the following: TTR of all symptoms, TTR of individual symptoms, time to cessation of viral shedding and time to resolution of fever. These endpoints will be summarized using Kaplan-Meier tables and graphs. Viral shedding will be studied also per virus strain. The median TTR and associated 95% CIs will be estimated for each of the two treatment groups. The exact CIs of the median differences of Hodges-Lehmann (HL) estimators will be derived using the PROC NPAR1WAY in SAS. The protocol mentioned bootstrapping, however in SAS, bootstrapping calculates differences between medians, when the correct estimator in skewed distributions is the median of differences (or HL estimator). Asymptotic theory exists to obtain those CI (aka Moses CI).

Patients who have not experienced the event, e.g. resolution of all symptoms, by the last day of contact will be censored at this time. Patients who withdraw from the study without experiencing the event will be censored at the time of withdrawal (see [Appendix 7](#)).

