- Area Under the Effect-Time Curve (AUE) for all symptoms (adults only). This will be calculated from baseline (symptom score prior to start of study drug or, if missing, before 12 h after starting treatment) to the time at which all symptoms are first alleviated, i.e. ≤ 1 . Totals scores will be tracked over time. The AUE of these average scores is then calculated for each subject using the trapezoidal rule. The median of those AUE will be compared between groups using CI.
- TTR of Individual Symptoms (all patients with baseline symptom scores > 1) is defined as the time from treatment initiation to the start of the 24 hour period at which a specific symptom score is ≤ 1 and remains ≤ 1 for at least 21.5 hours. For children, if a score of 4 (“do not know” or “not applicable”) occurs at any assessment during the study for any given symptom(s), the assessment will not be included in calculating the TTR. Patients with symptom scores ≤ 1 at baseline which remain ≤ 1 for at least 21.5 hours thereafter will have a TTR set to missing. Patients with symptom scores > 1 at baseline followed immediately by scores ≤ 1 for at least 21.5 hours will have a TTR set to zero.
- The AUE for Individual symptoms (adults only) will be calculated from baseline (symptom score prior to start of study drug) to the time at which the individual symptom is first alleviated (≤ 1). The AUE of the individual symptom score is calculated for each subject using the trapezoidal rule.
- Time to resolution of fever is defined as the time from treatment initiation to the last time at which temperature was $\geq 37.8^\circ\text{C}$ (all patients). For patients who did not have a temperature $\geq 37.8^\circ\text{C}$ at baseline and throughout the dosing period, the time to resolution of fever will be missing. For patients who had a temperature of $\geq 37.8^\circ\text{C}$ at baseline, followed immediately by a temperature of $< 37.8^\circ\text{C}$ at their first post-baseline assessment, the time to resolution of fever will be zero. Patients who still had a temperature $\geq 37.8^\circ\text{C}$ at the end of the follow-up period will be censored at that time point. Patients who withdraw prior to resolution of fever will be censored at the time of withdrawal.

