4.4.4.2 Efficacy Analyses excluding other antiviral patient data

The TTR (mITTi) of all symptoms analyses described in Section 4.4.2.1 will be rerun excluding any follow-up data collected from those patients who began treatment with another antiviral for influenza, on or after discontinuation of study drug. Note that although Section 8.2.7.1 of the protocol indicates that such exclusions should be made for all efficacy analyses, this statement contradicts the definition of the ITT, ITTi and mITTi populations, so the exclusions of antiviral patient data will be regarded as a sensitivity analysis rather than the main analysis. Non-immunocompromised patients will be excluded.

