If all non-missing baselines symptoms were > 1 at baseline and recovered (<=1) immediately and remained <=1 for at least 21.5 hours OR if all non-missing baselines symptoms were > 1 at baseline and no further recordings of symptom scores had been recorded, then the Time to Alleviation of All symptoms was 0.

[Corresponding Efficacy VAD variables TALLSYMP=0 and CENSORED=0]

For Paediatric studies, should a subject only have No/mild symptoms from baseline onwards, and subsequent visits satisfy the 21.5 hour rule, then set TALLSYMP=0 and CENSORED=0.

Subjects withdrawing prior to alleviation of symptoms were **censored** at the time of withdrawal. [denoted in the efficacy VAD as CENSORED=1]

The primary endpoint was compared between groups using statistical methodology appropriate for survival data since censored data is present. The within-treatment group summary measures of median duration, was estimated from the Kaplan-Meier curve. A weighted Mantel-Haenszel test was used to formally test for a between-treatment group effect since the proportional hazards assumption was considered unlikely to hold *a priori*.

The weighting scheme used was the generalised Gehan Wilcoxon weights in which the weighting is equal to the number in the risk set.

Kaplan-Meier graphs of duration of symptoms according to treatment group were provided. Estimates of the difference between median durations were provided by subtracting the observed treatment group medians obtained from the Kaplan-Meier curve and estimating between group variability through bootstrapping. The dataset was sampled 2000 times in order to provide 95% confidence intervals using the percentile method (Efron 1993).

The bootstrap methodology had previously been applied within the influenza clinical trial field by the MIST group (MIST 1998) when comparing time to alleviation of illness in subjects treated with inhaled Zanamivir or placebo.

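### The between-group difference for the censored time-to-event endpoints uses a Hodges-Lehmann interval that cannot take censoring, and no rule says how a censored time enters it

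*SAP*

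**What the plan says.** Section 4.4.2.1 covers time to resolution (TTR) of all symptoms and of individual symptoms, cessation of viral shedding and resolution of fever. Censoring is explicit: "Patients who have not experienced the event, e.g. resolution of all symptoms, by the last day of contact will be censored at this time", and withdrawals without the event are censored at withdrawal. Section 2.2.2.1 repeats this for fever: "Patients who withdraw prior to resolution of fever will be censored at the time of withdrawal".

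Each arm is summarised by Kaplan-Meier. For the difference between arms the section turns to another method: "The exact CIs of the median differences of Hodges-Lehmann (HL) estimators will be derived using the PROC NPAR1WAY in SAS". The note heading the table in Appendix 5 repeats Hodges-Lehmann with the Moses interval. The bootstrap named in the protocol is set aside because it compares medians, "when the correct estimator in skewed distributions is the median of differences (or HL estimator").

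Appendix 7, to which Section 4.4.2.1 refers for censoring, describes how the oseltamivir programme handled this endpoint: "The primary endpoint was compared between groups using statistical methodology appropriate for survival data since censored data is present". It adds "The weighting scheme used was the generalised Gehan Wilcoxon weights in which the weighting is equal to the number in the risk set", and, for the effect size, "Estimates of the difference between median durations were provided by subtracting the observed treatment group medians obtained from the Kaplan-Meier curve", with a percentile bootstrap interval.

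**The concern.** The Hodges-Lehmann estimate and the Moses interval are built from every difference between a patient in one group and a patient in the other. They are defined for fully observed times, and PROC NPAR1WAY has no place for a censoring indicator. A program therefore has to convert each censored time into something else, and the SAP does not say what. Section 4.9 covers only interpolation of missing scores and temperatures. Section 4.4.4.4 and Appendix 7 say when a time is censored, not how it enters this step.

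The stated reason for the change is skewness, which is a separate matter from censoring. The censoring-aware comparison in Appendix 7 is lost without comment.

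Section 4.4 says treatment differences will be reported with intervals only, so these intervals carry all the comparative efficacy information. Section 4.4.2.2 lists three median differences against matched placebo with 90% and 95% intervals, and Section 4.4.6.1 links the 90% intervals to a regulatory discussion of a possible new dose recommendation. Unequal follow-up is built into that comparison: Section 4.4.4.4 puts the last assessment at days 17 to 25 in the historical studies and at about day 40 here. Section 4.4.4.2 can add censored times, because the analysis "will be rerun excluding any follow-up data collected from those patients who began treatment with another antiviral for influenza"; this applies to patients unresolved when the other antiviral starts.

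**Working it through.** **The plan's own figure.** Section 2.3 gives 66% power for 75 per group, a difference of 34 h, SD 98 h and two-sided alpha 10%. With Wilcoxon efficiency 3/π, the effective n is 75 × 3/π = 71.6. The standardised difference is (34/98) × √(71.6/2) = 2.08, and Φ(2.08 − 1.645) is about 0.667. Noether's rank-sum formula gives 65.9%. The figure reproduces, and the calculation has no term for censoring.

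**Why censoring breaks the estimator.** The estimate is the median of X_i − Y_j over all m × n pairs. The interval runs between the c-th smallest and c-th largest differences, with c = mn/2 − z√(mn(m+n+1)/12). For m = n = 68 at 90%: 2312 − 1.645 × 229.8, so c = 1934. If X_i is censored at C_i, only X_i − Y_j > C_i − Y_j is known. Counting C_i as an event makes every such difference too small. Dropping the patient removes long illnesses preferentially.

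**Inputs to the simulation.**
- From the SAP: SD 98 h; follow-up to about day 40 here and days 17 to 25 after onset historically; 75 infected patients per arm; at least 15 paediatric patients. Taking adults only, 75 − 15/2 is about 68 per group.
- Assumed: log-normal times with median 144 h (log-SD 0.544 gives SD 98 h); withdrawal times uniform over days 0 to 10 and unrelated to illness; follow-up of 39 days here; 36 h from onset to treatment in the historical groups; independent groups. Each cell has 2000 trials (1500 for the n = 8 cells and for the -34 h shift at log-SD 1.0), with Monte Carlo error about 0.3 to 0.5 h.

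**Historical comparison, no true difference, SD 98 h.** Negative values favour the current study; 90% interval coverage is in brackets where available.

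| Withdrawal, current v historical | Realised censoring | Bias, as events | Bias, dropped |
|---|---|---|---|
| 5% v 5% | 3% v 5% | +0.3 h (89%) | +2.5 h (88%) |
| 10% v 5% | 6% v 5% | -2.6 h | +1.8 h |
| 15% v 5% | 10% v 5% | -5.8 h (87%) | +0.4 h (90%) |
| 25% v 5% | 16% v 5% | -12.1 h (75%) | -2.2 h (89%) |

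**Dose comparison, same SD.** Bias is 0.3 h at 5% v 5%; -3.1 h (as events) and -1.2 h (dropped) at 10% v 5%; -12.9 h and -4.8 h at 25% v 5%.

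**With a true shift of -34 h, historical.** The estimates are -32.5 h and -31.4 h at 5% v 5%, and -42.0 h and -37.2 h at 25% v 5%. The sign holds.

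**Longer tails than the SAP assumes** (log-SD 1.0, SD 311 h), 5% v 5%, historical. Dropping gives +16.9 h (coverage 76%), because the shorter historical follow-up loses more long illnesses. Counting as events gives only about +2.5 to +2.9 h (coverage 89%). Censoring at day 25, as in Section 4.4.4.4, cuts the dropped-patient bias to +6.7 h (88%) if Hodges-Lehmann is applied there.

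**A different model** (75 per arm, medians 134 h and 100 h, log-SD 0.9, true shift 28.1 h, 95% intervals). Counting censored times as events gave 39.4 h with 5% withdrawal in the slower arm and 25% in the faster (coverage 88%), and 12.3 h with the rates reversed (about 81%). Dropping stayed near 27 to 28 h when withdrawal was unrelated to illness length, but fell to 14.3 h (75%) when follow-up simply stopped at 240 h.

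**Censoring-aware alternatives.** In the Gehan statistic each pair scores +1, -1 or 0 according to whether the order of the two times is known. The shift estimate is the value that brings the statistic to zero. The interval is the set of shifts the test does not reject. In every 68-per-group cell it stayed within 1.0 h of the truth, with coverage 89% to 91%. Differences in Kaplan-Meier medians stayed within 2.1 h.

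**The case against.** The strongest reply concerns weight. Efficacy is secondary, no hypothesis is tested, and Section 4.4.2.2 concedes that the historical difference cannot separate immune status from drug effect. Appendix 5 also shows Kaplan-Meier medians by group, which handle censoring. For shedding, Section 2.2.2.3 counts later missing values as negative, which limits censoring. At SD 98 h and low, balanced withdrawal the bias is small beside a 90% interval width of 42 to 43 h, and nothing in the SAP points to 25% v 5%. All of this stands and limits the severity.

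Appendix 7 reserves a missing time mainly for patients without qualifying baseline symptoms and flags withdrawals separately. Counting censored times as events is therefore the likelier reading, and under it the +16.9 h figure does not arise. That is fair, but the as-events coding is the one most damaged by unequal withdrawal. Ranking censored times beyond all events is a third coding; it did no better under imbalance.

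Appendix 7 describes past practice, and Section 4.4.2.1 openly replaces the bootstrap. That is true, but the reason it gives does not cover censoring.

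The simulations treat groups as independent and withdrawal as unrelated to illness, whereas the main historical comparison is matched 1:1. The sizes are illustrations, not predictions.

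**Conclusion.** The point holds and should be fixed. The estimator named for the between-group difference does not fit endpoints the SAP itself right-censors, and the handling of censored times is left to programming. Followed as written, the plan can give a biased difference and an interval that under-covers.

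The size depends on assumed withdrawal. At the SAP's SD it runs from 0.3 to 2.5 h in the historical comparison at 5% in both groups, up to about 12 h with 75% coverage at 25% v 5% if censored times count as events. The randomised dose comparison is little affected when censoring is low and balanced. Per-arm Kaplan-Meier medians and both co-primary objectives are untouched.

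**What to change.** In Section 4.4.2.1 and the Appendix 5 note, replace the NPAR1WAY interval for censored endpoints with one censoring-aware difference and interval, fixed before unblinding:

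- **(a) Preferred:** a Hodges-Lehmann-type shift obtained by inverting a Gehan-Wilcoxon test over a grid of shifts. It keeps the shift estimand the SAP wants and uses the weights Appendix 7 names.
- **(b) Alternative:** the difference in Kaplan-Meier medians with a percentile bootstrap interval, as in Appendix 7. This returns to the estimand Section 4.4.2.1 rejected.

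Report the number censored in each group beside every difference. If the NPAR1WAY output is kept, make it supportive, with a written rule for censored times.

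The cost is SAP wording and one validated macro applied across the censored endpoints; no new data are needed. Median 90% interval widths for (a) are 42 to 43 h at SD 98 h, the same as Hodges-Lehmann, and 65 to 67 h against 61 to 65 h at log-SD 1.0. Option (b) widens them to 56 to 59 h and 103 to 110 h. With about 8 children per arm, intervals are wide either way: 135 to 137 h for (a), 160 to 167 h for (b). Like Hodges-Lehmann, (a) assumes a location shift; if that fails, the estimate depends on the censoring pattern.

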4.4.4.4 Comparison of TTR of All Symptoms to Historical Control

The following Kaplan-Meier analyses will be carried out using the mITTi population to support the comparison of Study NV20234 treatment response with the historical placebo response with both 1:1 and 1:>1 ratios:

- The TTR of all symptoms for adults using only follow-up symptom data recorded up to and including 25 days compared with historical placebo data. This is to investigate the impact of differences in the follow-up observation periods between study NV20234 and the oseltamivir treatment database. Adult patients in Study NV20234 who have not experienced resolution of symptoms by day 25 will be censored on day 25. In the historical studies (see section 4.4.2.2 above and [appendix 4](#)) the final assessment was between days 17 and 25 post onset. A sensitivity analysis will be carried out comparing results from the previous analyses against an analysis without censoring at 25 days, i.e. using the current final assessment ~40 days after onset of symptoms.
- The TTR of all symptoms for patients who had symptoms onset ≤ 48 hours before first dose, for each active treatment group and combined, compared with matched historical control patients.

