Previous/Concomitant medications	x	←—————→							
Adverse Events/Sec Illnesses and Treatments		←—————→							
Rejection, Graft versus host disease (GVHD)		←—————→							

- a. Urine pregnancy test for patients of child-bearing potential according to the judgment/discretion of the investigator.
- b. Hematology (CBC with differential) and chemistry (AST, ALT, total bilirubin, urea, Cr). Serum creatinine testing may be done at a local laboratory when clinically indicated to calculate creatinine clearance.
- c. Baseline swab samples will be assessed for the presence of resistance mutations.
- d. Two nasal and one throat swab for viral culture and RT-PCR.
- e. Influenza symptoms, temperature, and date/time of oseltamivir dose will be recorded by the patient in the patient diaries twice daily on Days 1 – 10, and once daily thereafter.
- f. A home visit may be made on Day 2 or 3 (for patients who are too ill to come into the clinic) and/or, Day 6, and/or Day 8; however, it is recommended that the PK blood draw be performed at the clinic.
- g. Day 2/3 visit window = + 1 day. Day 6 visit window = ± 1 day; Day 8 visit window = + 1 day. Day 11 visit window = ± 1 day. Day 15 and Day 40 visit occur approximately 5 and 30 days after the last dose respectively. Day 15 window = ± 1 day. Day 40 window ± 2 days.

- h. Only weight to be assessed. Height is not necessary at this visit. Study drug is taken on Day 11, only if the first dose was taken after 4 p.m. on Day 1.
- i. Patients who are rapid diagnostic positive can be treated per standard of care. They will be required to come for their follow-up visits on Day 15 and Day 40.
- j. Patients who discontinue treatment prematurely will have an end of treatment (Day 11) assessment at the time of treatment discontinuation or the following day. They will be required to attend their follow up visits approximately 5 and 30 days after the last dose (Day 15 and Day 40 assessments).
- k. Patients who discontinue during follow-up will have an end of follow-up (Day 40) assessment. This visit must occur within 30 days of the last dose.
- l. For patients who are unable to attend the clinic, swabs may be taken at home on those days where there is a home visit by site personnel.
- m. Plasma PK samples for assessment of oseltamivir and oseltamivir carboxylate will be collected from patients who give additional consent to participate in PK sampling using a sparse PK sampling approach.

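### Unresolved symptom times are censored at last contact (or at Day 25) instead of the last diary entry, which slows the Kaplan-Meier curve when patients stop the diary

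*SAP*

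**What the plan says.** SAP 4.4.2.1 covers time to resolution (TTR) of all symptoms, of individual symptoms and of fever, and cessation of shedding. Its general rule is "Patients who have not experienced the event, e.g. resolution of all symptoms, by the last day of contact will be censored at this time". The last day of contact is not defined. For withdrawals it adds: "Patients who withdraw from the study without experiencing the event will be censored at the time of withdrawal".

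SAP 4.4.4.4, the Day 25 analysis against historical placebo, says: "Adult patients in Study NV20234 who have not experienced resolution of symptoms by day 25 will be censored on day 25".

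Appendix 7 announces rules for subjects who withdrew or stopped recording before alleviation. The only censoring date it gives is for withdrawal: "Subjects withdrawing prior to alleviation of symptoms were" censored when they withdrew.

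On observation, Appendix 2 footnote e says that symptoms "will be recorded by the patient in the patient diaries twice daily on Days 1 – 10, and once daily thereafter". Footnote g says: "Day 15 and Day 40 visit occur approximately 5 and 30 days after the last dose respectively". Footnote j requires patients who stop treatment early to attend those two visits as well.

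Two other rules treat absent data in the opposite way. Appendix 7 sets TTR to 0, as an event, when all non-missing baseline symptoms exceed 1 and nothing is recorded afterwards. Section 2.2.2.3 takes later missing culture or RT-PCR results as negative.

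**The concern.** A Kaplan-Meier estimate assumes that everyone in the risk set could be seen to have the event. For symptoms, the diary is the only source. Site contact does not depend on it, so the censoring date can fall weeks after the last symptom score. During that gap the patient counts as still symptomatic, although nobody knows whether that is so.

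Interpolation (section 4.9 and Appendix 7) does not close the gap, because it needs a later assessment and a patient who stops for good has none.

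The effect is to make resolution look slower, by an amount set by diary compliance and not by the drug. If stopping differs between the dose groups, or between this trial and the matched historical patients, the comparison is distorted too.

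**Working it through.** **The SAP's own figure.** Section 2.3 states 66% power for 75 per group, a difference of 34 h, an SD of 98 h and a two-sided alpha of 10%. With the Wilcoxon efficiency 3/π, the effective n is 75 × 3/π = 71.6. Then √(71.6/2) × 34/98 − 1.645 = 0.43, and Φ(0.43) is about 66.7%. Noether's formula gives 65.9%. The figure is reproduced, and nothing below depends on it.

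**Gap implied by the schedule.** Take a diary that stops on Day 12 with attendance at Day 40. The patient is at risk without symptom data for 40 − 12 = 28 days, or 25 − 12 = 13 days under the Day 25 rule.

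**Direction.** S(t) = ∏(1 − dᵢ/nᵢ). A patient who has stopped recording cannot enter dᵢ but stays in nᵢ. If all such patients are held to Day 25 or Day 40, nobody leaves the risk set earlier except by an event. The curve then reduces to 1 − P(T ≤ t and T ≤ stop time), which lies above the true S(t).

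**Size, model A (assumed).** Log-normal TTR with median 120 h and log SD 0.9. Stopping times are exponential, tuned so that the stated share stops while unresolved before Day 40 (960 h). Stopping is unrelated to outcome.

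| Share stopping unresolved | Median, last diary | Median, Day 40 | 75th percentile, last diary | 75th percentile, Day 40 |
|---|---|---|---|---|
| 5% | 120 h | 123 h | 219 h | 235 h |
| 10% | 120 h | 126 h | 219 h | 257 h |
| 15% | 120 h | 130 h | 219 h | 291 h |
| 20% | 120 h | 135 h | 219 h | 365 h |

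Censoring at Day 25 (600 h) gives the same shifts, because these quantiles fall before Day 25. Comparing the analyses with and without Day 25 censoring, as 4.4.4.4 plans, would therefore not reveal the problem.

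**Size, model B (assumed).** Exponential TTR with median 120 h; 10%, 20% or 30% of patients are given a stop time uniform on 24 to 240 h, so that 5%, 10% or 15% stop unresolved. Last-diary censoring keeps the median near 120 h and the 75th percentile near 240 h. Day 40 or Day 25 censoring gives medians of about 123, 126 and 129 h, and 75th percentiles of about 260, 289 and 338 h.

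Hand check of the 20% case at t = 125.5 h:
- F(t) = 1 − 2^(−125.5/120) = 0.516.
- The mean of F over stop times from 24 to 125.5 h is 1 − (120/ln 2)(0.8706 − 0.4844)/101.5 = 0.341.
- Observed resolution among stoppers is (114.5/216)(0.516) + (101.5/216)(0.341) = 0.434.
- Overall, 0.8 × 0.516 + 0.2 × 0.434 = 0.50, so the late-censored median is about 125.5 h.

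**The between-group difference.** Section 4.4.2.1 takes the Hodges-Lehmann difference from PROC NPAR1WAY. That procedure has no censoring indicator, so a censoring time enters as if it were the TTR. With identical true TTR in both arms:

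| Model | Stopping, arm 1 vs arm 2 | Shift, Day 40 | Shift, last diary |
|---|---|---|---|
| B | 10% vs 10% | about 0 | about 0 |
| B | 10% vs 20% | +6.4 h | −3.5 h |
| B | 5% vs 20% | +7.7 h | −6.5 h |
| A | 10% vs 20% | about +7 h | about −9 h |
| A | 5% vs 20% | about +15 h | about −13 h |

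Moving the censoring date repairs the Kaplan-Meier summaries. With unequal stopping, the Hodges-Lehmann bias changes sign but does not disappear.

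**The case against.** Several stronger readings are tempting, and the SAP does not support them.

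- **Everyone who stops recording counts as ill.** Not so. A patient with all non-missing baseline symptoms above 1 and no later entry becomes an event at time 0 under Appendix 7, which biases the other way. For withdrawals, a gap exists only if the diary stopped before the withdrawal date.
- **Shedding is affected in the same way.** Not established. If the missing-swab rule in 2.2.2.3 covers every later missing value, a patient whose swabs stop becomes an event. If it covers only values after a first negative, the last-contact rule applies. The SAP does not say which.
- **Fever is affected in the same way.** Section 2.2.2.1 gives fever its own censoring rule, and temperature is also taken at site visits through Day 40, so it stays observable without a diary.
- **A false difference between doses can be set against 34 h.** Section 2.3 defines 34 h for active treatment against historical placebo, not for one dose against the other.
- **The historical comparison is biased against this trial.** Section 4.4.4.4 already addresses the difference in follow-up, and Appendix 7 describes an algorithm for the whole Tamiflu program. The SAP does not show that historical patients were handled differently.

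The Day 25 sentence can also be read charitably: the same bullet limits the analysis to symptom data recorded up to Day 25, and 4.4.2.1 already censors withdrawals at withdrawal. That is probably the intent. As written, though, the sentence moves an adult who withdrew unresolved on Day 6 to Day 25, which conflicts with 4.4.2.1.

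It is also fair that the magnitude rests on assumed stopping rates, and that a large imbalance between arms is not expected in a double-blind trial. What survives is the group that records after baseline, stops while symptomatic and stays in contact. For them, the stated rule gives a censoring date with no data behind it.

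**Conclusion.** The point holds for TTR of all and of individual symptoms. Following 4.4.2.1, or 4.4.4.4 literally, biases the Kaplan-Meier curve and median towards slower resolution. For a true median of 120 h and random stopping of 5% to 20% while unresolved, the median rises by about 3 to 15 h, and the upper part of the curve moves more. The distributions and stopping rates are assumptions; the actual size is unknown because the SAP gives no diary-stopping rate. If diaries are nearly complete, the effect is negligible.

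A reader might infer that the trial's conclusions are at risk. The SAP does not support that: the co-primary endpoints are safety and resistance, and all efficacy endpoints are secondary or exploratory with no formal hypothesis. The correction is worth making because these medians carry the dose and historical comparisons and the change is cheap.

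**What to change.** 1. **4.4.2.1:** *For TTR of all and of individual symptoms, patients without the event, including withdrawals, are censored at their last evaluable diary assessment.*
2. **4.4.4.4:** *Unresolved adults are censored at the earlier of the last evaluable diary assessment and Day 25.*
3. **Historical patients:** apply the same rule where diary-level data allow, and state where they do not.
4. **Appendix 7:** add the rule for patients who stop recording without withdrawing, and reconcile it with the rule that sets TTR to 0 as an event when no post-baseline scores exist.
5. **2.2.2.3:** state whether missing swabs are taken as negative only after a first negative result, and give the censoring date for a patient whose last available swab was positive.
6. **Between-group difference:** report a censoring-aware estimate as well, such as the difference in Kaplan-Meier medians with the bootstrap interval described in Appendix 7. Section 4.4.2.1 gives a reason for preferring Hodges-Lehmann to the bootstrap, so this can stand beside it. Without it, items 1 and 2 correct the Kaplan-Meier summaries but not the reported difference.

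The cost is SAP wording, a small amount of derivation work and one extra estimate, with no new data from this trial. Re-deriving historical times could take more work, depending on what diary data are available. The downside is slightly more early censoring.
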